10.2 Study Populations

The following study populations will be examined:

Modified Intention to Treat (mITT): All randomized patients who received at least 1 dose, complete or incomplete, of study medication

Safety population (SP) = mITT population

Per protocol (PP) population: All randomized patients who received study treatment according to randomization and did not have major disqualifying protocol violations.

Major protocol violations will be stated in the statistical analysis plan (SAP).

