7.1 Clinical Examinations and Procedures prior to Therapy (Pre-Screening / Baseline)

The baseline examinations should be performed within 28 days before start of treatment, except laboratory parameters and urine pregnancy test (β -hCG), which should be assessed within 3 days before registration:

- Informed Consent
- Demographic data, medical history
- Previous and concomitant medication within the last 2 weeks before signing of informed consent
- *RAS* mutation analysis on tumor tissue
- Blood sample (20 ml) for liquid biopsy
- TNM-staging at first diagnosis
- CT-scan of abdomen, chest and pelvis to document baseline tumor status (in case of contraindications to CT scan, e.g. allergy to contrast medium, MRI should be performed); current TNM staging
- Vital signs: body temperature, heart rate, blood pressure, height and weight
- ECG
- Echocardiography
- ECOG performance status assessment
- Hematological and biochemical laboratory assessment including hemoglobin, thrombocytes, neutrophils, Na^+ , K^+ , Mg^{2+} , Ca^{2+} , ASAT, ALAT, alkaline phosphatase, GGT, bilirubin, urea, creatinine, creatinine-clearance, C-reactive CRP, CEA, CA-19-9
- Test for DPD deficiency as specified in the 'red-hand-letter' for 5-FU (i.v.), capecitabine- and tegafur-containing drugs, dated 04.06.2020:
 - Genotyping (4 variants of the DPYD genotype, namely c.1905+1G>A, c.1679T>G, c.2846A>T und c.1236G>A/HapB3, are associated with a high risk for severe toxicities)
 - and/or
 - Phenotyping (a blood uracil level between ≥ 16 and < 150 ng/ml is an indicator of partial DPD deficiency, a blood uracil level ≥ 150 ng/ml is an indicator of complete DPD deficiency)
- Coagulation parameters: INR, aPTT
- Hepatitis B and C serology
- Females of childbearing potential: urine pregnancy test (β -hCG)

Female patients of childbearing potential as well as all men must be informed that they are obliged to practice medically accepted contraception throughout the study.
- Adverse events
- Administration of 1 or 2 cycles of study treatment (FOLFIRI or mFOLFIRI) are permitted before *RAS* status is available. In case of *RAS* wild-type, patients are defined as screening failures and will not be treated further in the study.

7.2 Clinical Examinations and Procedures during Pre-randomization (Screening) Phase for conversion to RAS wild-type (maximum time period of 16 weeks from start of FOLFIRI)

Prior to every cycle (within 48 h before administration of study treatment):

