- Hematological and biochemical laboratory assessment including hemoglobin, thrombocytes, neutrophils, Na^+ , K^+ , Mg^{2+} , Ca^{2+} , ASAT, ALAT, alkaline phosphatase, GGT, bilirubin, urea, creatinine, creatinine-clearance, C-reactive CRP, CEA, CA-19-9

Prior the first cycle (within 72 h before administration of study treatment):

- Females of childbearing potential: urine pregnancy test (β -hCG)

Prior to administration of study treatment:

- Assessment of ECOG performance
- Survey of concomitant medication
- Vital signs: body temperature, heart rate, blood pressure, and weight

Every 2 weeks:

- Administration of study treatment (FOLFIRI or mFOLFIRI)
Patients with partial DPD deficiency should receive the first cycle with a reduced 5-FU dose. Dose reduction and escalation are at the discretion of the investigator and must be determined in the best interest of the patient.

Every 4 weeks:

- Females of childbearing potential: urine pregnancy test (β -hCG)

After every cycle:

- Assessment of adverse events. Adverse events are recorded according to NCI-CTCAE v.5.0. Serious adverse events have to be reported within 24 h to Alcedis GmbH (section 9.6)

Every 8 weeks:

- Tumor assessment using CT-scan (in case of contraindications to CT scan, e.g. allergy to contrast medium, MRI should be performed) and classification of the response according to RECIST-Criteria V 1.1; the same method should be used throughout the study

At week 4, 8, 12 and 16 (until conversion to RAS wild-type):

- Blood sample (20 ml) for liquid biopsy

If clinically indicated: ECG

For patients without conversion to RAS wild-type by week 16, the 'end of study'-form must be completed.

Patients with conversion of RAS mutation to RAS wild-type, by ≤ 8 weeks or by > 8 weeks, will be randomized at week 8 or 16 respectively. Before randomization, the inclusion / exclusion criteria have to be checked.

For the first 20 patients with *RAS* wild-type in liquid biopsy: New tumor biopsy, if possible, with *RAS* analysis. Overall, in at least 80% of patients a biopsy should be taken to confirm *RAS* status in tissue of respective patients.

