8.5 Best Overall Response According to RECIST Criteria

Target lesions	Non-target lesions	New lesions	Overall response
CR	CR	No	CR
CR	SD	No	PR
PR	SD	No	PR
SD	SD	No	SD
PD	any	Yes or No	PD
any	PD	Yes or No	PD
any	any	Yes	PD

9 Assessment of Safety

Toxicities will be defined according to the Common Terminology Criteria for Adverse Events (CTCAE) version 5.0 (Appendix 17.3).

The investigator is responsible for documenting all adverse events that occur during the study. Adverse events have to be reported after informed consent until 30 days after last dose of study treatment. Then only adverse events which are causally related to study treatment have to be reported.

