10.1.2 Secondary Variables

- OS, defined as time from date of randomization until death from any cause; OS should be censored, in patients without an OS event, on the last date they were known to be alive.
- TFTS, is defined as time from date of randomization to failure of treatment strategy defined as treatment discontinuation for any reason, including disease progression, withdrawal of consent, treatment toxicity, patient preference, loss to follow up or death from any cause.
- PFS rate 1 year after date of randomization, derived by Kaplan-Meier method (defined as the estimated rate of patients with progression or death from any cause 1 year after date of randomization)
- Depth of response (DpR) in terms of reduction of tumor mass in experimental and control arms, defined as the percentage of tumor shrinkage, based on longest diameters of all target lesions or reconstructed volume, observed at the lowest point (nadir) compared to baseline. The time for DpR assessment varies between patients relating to the individual achievement of maximal tumor shrinkage, which typically occurs 4–6 months after the start of 1st-line therapy. DpR varies between 100% (= all target tumor lesions have disappeared) and 0% (=no change in tumor size) and has a negative value in cases of increased tumor volume.
- Percentage of patients with metastasis resections, defined as percentage of patients with complete resection of primary tumor and metastases (R0-resection), at any time after the start of 1st line therapy until the end of the treatment strategy.
- ORR, defined as the proportion of randomized patients with CR or PR as best response since start of 1st line therapy.
- Safety, defined as all SAEs regardless of causality, and non-serious adverse events according to CTCAE Version 5.0 criteria, that are definitely, probably, or possibly related to the administration of any study treatment, or that cause permanent discontinuation of treatment, recorded from the date of signature of Informed Consent.

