10.3 Statistical Methods

In general summary statistics (n, mean, standard deviation, median, minimum and maximum for continuous variables, and number of patients and percentage in each category for categorical variables) will be provided.

Time to event variables will be summarized using Kaplan-Meier methods as well as a Cox-regression model taking into account the following stratification factors: conversion to RAS wildtype within the first 8 weeks from start of 1st line therapy or later. Other factors (such as e.g. ECOG PS or location of metastases) will be taken into account in a multivariable Cox regression as well. Details will be specified in the SAP.

All analyses except for the log-rank test for the primary endpoint will be of exploratory manner. Hence no adjustment of the type I error rate is necessary.

All efficacy variables (primary and secondary endpoints) will be analyzed in the mITT and the PP set.

The SP set will be used for the analyses of the safety variables. Safety analysis includes:

- System Organ Class (SOC) and Preferred Terms (PT) according to the Medical Dictionary for Regulatory Activities (MedDRA). The most current MedDRA version, which is valid at the time of analysis, will be used.
- Causality of AE
- Outcome of AE
- AEs leading to death
- AEs leading to treatment/study discontinuation
- All SAEs

Details of the analyses will be given in the SAP.

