### 3.2 Analysis populations

**Modified Intention to Treat (mITT):** All randomized patients who received at least 1 dose, complete or incomplete, of study medication.

**Safety population (SP)** = mITT population.

**Per protocol (PP) population:** All randomized patients who received study treatment according to randomization and did not have major disqualifying protocol violations, i.e., did not violate any selection criterion.

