**(Optionally) Table 4.1: AEs - overview**

Overview	5-FU [N, %]	Folinic acid [N, %]	Irinotecan [N, %]	Cetuximab [N, %]	Total [N, %]
Number of patients in mITT					
Patients with any AE					
Patients with AEs by maximal grade					
Grade 1					
Grade 2					
Grade 3					
Grade 4					

Grade 5							
Number of AEs							
Patients with treatment-related AEs							
Number of treatment-related AEs							
Patients with any SAE							
Patients with SAEs by seriousness criteria							
Death							
Life-threatening							
Hospitalization							
Persistent or significant disability/incapacity							
Congenital anomaly/birth defect							
Important medical event							
Number of SAEs							
Patients with any special AE							
Patients with special AEs by speciality criteria							
Pregnancy							
Medication error							
Number of special AEs							
Patients with AEs leading to discontinuation							
Number of AEs leading to discontinuation							

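### The safety population is limited to randomised patients, so patients given study FOLFIRI but never randomised fall outside the safety analysis set

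*Protocol*

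**What the plan says.** Protocol 10.2 defines the safety set in one line: "Safety population (SP) = mITT population". The mITT, in the same section and again in SAP 3.2, is "All randomized patients who received at least 1 dose, complete or incomplete, of study medication". Protocol 10.3 then commits the safety analysis to that set: "The SP set will be used for the analyses of the safety variables". Neither document defines a set of all treated patients.

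Other sections describe a wider treated group:

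- Protocol 7.1: "Administration of 1 or 2 cycles of study treatment (FOLFIRI or mFOLFIRI) are permitted before" the RAS result is known. Protocol 7.2 lists fortnightly FOLFIRI or mFOLFIRI in the pre-randomisation phase as study treatment, with adverse events assessed after each cycle.
- Protocol section 9, opening paragraphs: "Adverse events have to be reported after informed consent until 30 days after last dose of study treatment".
- Protocol 10.1.2: the safety variable covers all SAEs, plus non-serious events that are related to any study treatment or that end treatment permanently, "recorded from the date of signature of Informed Consent".

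In the SAP, Table 1 shows mITT and safety population as one row, and the first row of optional Table 4.1 is "Number of patients in mITT". SAP 4.2 says the analysis populations will not be distinguished. SAP 4.3.9 promises that all adverse events will be listed by patient number.

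**The concern.** The safety variable and the safety set do not match. The variable starts at consent and counts events under any study treatment, including those that end treatment. The set admits a patient only once randomised, at week 8 or 16. A patient who starts study FOLFIRI and leaves before then can meet the variable but cannot enter the set used to analyse it.

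Non-randomisation is part of the design. Patients who have not converted by week 16 leave the study (Protocol 7.2). Patients with progression are not randomised (3.1.2). Among the first 20 converters, discordant tissue and liquid results also rule out randomisation (3.1).

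What is at stake is the description of FOLFIRI toxicity. Under the plan it would be summarised only in patients who converted and reached week 8 or 16 without progression, although they are not the only patients who received the drugs and had events recorded.

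**Working it through.** **Inputs**

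- Planned conversion rate 80%, 144 screened, 116 randomised (Protocol 10.4). Section 3.1.4 describes the 144 as patients enrolled into the pre-randomisation phase, where FOLFIRI is given.
- Conversion of about 70% in the cited longitudinal data (Protocol 2.4).
- Conversion below 50% after 50 screened patients prompts DSMB recommendations (Protocol 2.7 and 10.5).
- Screening lasts up to 16 weeks with 14-day cycles, so up to 16 / 2 = 8 cycles per patient before randomisation.

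**Reproducing the plan's figure.** Number to enrol = 116 / conversion rate = 116 / 0.80 = 145, against the stated 144 (144 × 0.80 = 115.2). The figure reproduces to within one patient.

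**Treated patients outside the safety set.** Excluded = enrolled − 116, with enrolled rounded up.

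| Scenario | Enrolled | Outside the set | Share |
|---|---|---|---|
| Plan as stated | 144 | 144 − 116 = 28 | 28/144 = 19.4% |
| 80%, exact | 116/0.80 = 145 | 29 | 20% |
| 70% (background) | 116/0.70 → 166 | 50 | 30% |
| 50% (DSMB threshold) | 116/0.50 = 232 | 116 | 50% |

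These rows count non-converters only.

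**Progression before randomisation.** The documents give no rate. As an assumption, let a share p of converters progress first, at 80% conversion. Enrolled = 116 / (0.80 × (1 − p)):

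- p = 5%: 116/0.76 → 153, so 37 outside (24%)
- p = 10%: 116/0.72 → 162, so 46 outside (28%)
- p = 20%: 116/0.64 → 182, so 66 outside (36%)

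**Collection window.** Footnote 13 to the visit schedule starts event reporting at the first study treatment, whereas section 9 and 10.1.2 start it at consent. Both windows cover the pre-randomisation cycles, so the result is the same either way.

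**The trial as it closed.** SAP 4.2 reports seven patients. It does not say how many were randomised, so no number can be put on the actual loss.

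**The case against.** The best defence is that the set fits the stated objective. Safety is to be described in the experimental and control arms, and for that a randomised, treated set is natural. Everyone in it passed the same selection before allocation, so the comparison between arms is not biased by it. That stands. It does not settle the matter, because no AE table in the SAP is laid out by arm. Table 4.1 has columns for 5-FU, folinic acid, irinotecan, cetuximab and total; Tables 4.2 and 4.3 are pooled by CTCAE grade. Never-randomised patients received the first three drugs but are missing from the stated denominator.

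A reader might infer that serious events in these patients vanish. The documents do not support that. SAEs go to the study office within 24 hours whatever the analysis set (Protocol 9.6), and Protocol 5.4.3 provides ongoing safety review by the sponsor and DSMB. SAP 4.3.9 lists all adverse events without a population filter, so never-randomised patients may well appear in Listings 28.1 and 28.2. The SAP does not confirm it.

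A reader might also infer that all three optional tables exclude these patients. Only Table 4.1 names the mITT; the mock-ups of 4.2 and 4.3 name no set.

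Finally, it is tempting to say that early toxicity dropouts are the ones mainly lost. Some could be, but the 28 comes from assumed non-conversion, which is a ctDNA result. The documents give no rate of stopping for toxicity before randomisation.

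**Conclusion.** The gap is real but limited: it concerns the analysis set and its denominators. Applied as written, the plan leaves 28 of 144 patients (19%) who entered the study-treatment phase outside the safety population. The share is about 30% at the conversion rate in the protocol's own background and 50% at the DSMB threshold. This assumes that each enrolled patient received at least one dose. Progression or discordant biopsies before randomisation would add to the count.

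Safety oversight and the contrast between randomised arms are untouched. For the seven patients actually enrolled the loss may be zero; the documents do not allow it to be calculated. The listings may already cover everyone, in which case part of the remedy is only to say so. This is a cheap improvement.

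**What to change.** - Define the safety population in Protocol 10.2 and SAP 3.2 as all patients who received at least one dose of study treatment, including FOLFIRI or mFOLFIRI before randomisation. Separate it from the mITT in SAP Table 1.
- State in SAP 4.3.9 that Listings 28.1 and 28.2 and optional Tables 4.1 to 4.3 cover that set, and replace the mITT denominator in Table 4.1.
- Show non-randomised patients separately from Arms A and B, and flag events that start before randomisation so that they are not attributed to an arm.
- Keep the randomised set for efficacy and for the safety contrast between arms.

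The cost is a modest re-layout of the optional AE tables. One added column would not do it, because the present columns are drugs or grades. The protocol already requires collection of the adverse event data, so nothing new has to be recorded.

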10.3 Statistical Methods

In general summary statistics (n, mean, standard deviation, median, minimum and maximum for continuous variables, and number of patients and percentage in each category for categorical variables) will be provided.

Time to event variables will be summarized using Kaplan-Meier methods as well as a Cox-regression model taking into account the following stratification factors: conversion to RAS wildtype within the first 8 weeks from start of 1st line therapy or later. Other factors (such as e.g. ECOG PS or location of metastases) will be taken into account in a multivariable Cox regression as well. Details will be specified in the SAP.

All analyses except for the log-rank test for the primary endpoint will be of exploratory manner. Hence no adjustment of the type I error rate is necessary.

All efficacy variables (primary and secondary endpoints) will be analyzed in the mITT and the PP set.

The SP set will be used for the analyses of the safety variables. Safety analysis includes:

- System Organ Class (SOC) and Preferred Terms (PT) according to the Medical Dictionary for Regulatory Activities (MedDRA). The most current MedDRA version, which is valid at the time of analysis, will be used.
- Causality of AE
- Outcome of AE
- AEs leading to death
- AEs leading to treatment/study discontinuation
- All SAEs

Details of the analyses will be given in the SAP.

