Statistical hypothesis and sample size calculation	It is assumed that the difference in PFS at 12 months between the experimental and control arms will amount to 20%, which means an increase from 30% to 50% (Hazard ratio = 0.5757). Data from historical studies suggest the 12-months PFS rate of FOLFIRI in RAS -mutant mCRC to be in a range of 25-27%. In the CRYSTAL study PFS-rate at 12 months of FOLFIRI + Cetuximab in left-sided RAS wild-type mCRC was 50% (HR = 0.56). With a two-sided alpha error of 5% (0.05) and beta error of 20% (0.2) 2 x 58 patients are to be randomized and 107 PFS events are needed to achieve a power of 80%. With a recruitment period of 18 months, a drop-out rate of 0.25% per month the 107 events are expected after a total follow-up time of 52 months assuming an exponential distribution.
--	--

Schedule of visits and assessments

Patients	All patients		Randomized patients (Experimental arm)			Randomized patients (Control arm)			End of therapy	Follow- up
Trial period	Pre-Screening / Baseline	Pre-randomization (Screening) Phase (for conversion to RAS wild-type)	Switch arm (FOLFIRI/mFOLFIRI + cetuximab -> FOLFIRI/mFOLFIRI -> FOLFIRI/mFOLFIRI + cetuximab -> etc)			FOLFIRI/mFOLFIRI			Final Assessment	FU**
Scheduling window	-28 - -1 days	From Months 1 to 4	Every 2 weeks ± 3 days	Every 4 weeks ± 3 days	Every 8 / 12 weeks ± 3 days*	Every 2 weeks ± 3 days	Every 4 weeks ± 3 days	Every 8 / 12 weeks ± 3 days*	30± 2 days after last treatment	3 months ± 7 days
Procedures / Assessments										
Written informed consent	X									
Inclusion/Exclusion Criteria	X	X (before randomization)								
RAS mutation analysis on tumor tissue	X	X (New tumor biopsy at conversion, if possible, for the first 20 patients with conversion to RAS wild-type in liquid biopsy)***								
20 ml blood sample for liquid biopsy with RAS mutation analysis	X ¹	X ²	X ² (until week 8 for the first 10 patients)	X ² (until week 8)	X ² (from week 16 on)			X (week 8 / 24 only)		
Vital signs ³	X	X (before study treatment administration)	X			X				

Patients	All patients		Randomized patients (Experimental arm)			Randomized patients (Control arm)			End of therapy	Follow-up
Trial period	Pre-Screening / Baseline	Pre-randomization (Screening) Phase (for conversion to RAS wild-type)	Switch arm (FOLFIRI/mFOLFIRI + cetuximab -> FOLFIRI/mFOLFIRI -> FOLFIRI/mFOLFIRI + cetuximab -> etc)			FOLFIRI/mFOLFIRI			Final Assessment	FU**

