3.1.2 Randomization

All enrolled patients with conversion of mutant *RAS* as estimated centrally by liquid biopsy of cfDNA within the first 4 months (weeks 4 to 16) and without PD as determined by CT scan will be randomized at week 8, for patients converting at week 4 or 8, and at week 16 for patients converting at week 12 or 16 directly after the CT scan in a 1:1 ratio to either experimental Arm A (switch arm) or control Arm B. Patients with progressive disease before the randomization will not be considered for randomization.

The randomization lists will be kept in safe and confidential custody at Alcedis GmbH.

Stratification factors for randomization are:

- Conversion to *RAS*-wt: ≤ 8 weeks vs. > 8 weeks

Randomization of a patient during pre-randomization phase will be performed automatically, at weeks 8 or 16, if centrally assessed *RAS* wild-type in liquid biopsy is documented by the central analysis laboratory before 8 weeks or after 8 weeks, respectively, and there is no disease progression at that time. Randomization result is notified immediately by an automatically generated fax to the investigator.

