3.1.4 Number of Patients

Estimated number of patients enrolled into pre-randomization phase (conversion rate of 80%): 144

Number of randomized patients: 116 (58 patients in each arm) with 107 required events.

The screening will be continued until randomization of 116 patients.

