10.4 Sample Size

Data from historical studies suggest the 12-months PFS rate of FOLFIRI in RAS-mutant mCRC to be in a range of 25-27%. In CRYSTAL study PFS-rate at 12 months of FOLFIRI + Cetuximab in left-sided RAS wild-type mCRC was 50% (HR = 0.56).

Assuming that the difference in PFS at 12 months between the experimental and control arms will amount to 20%, which means an increase from 30% to 50% (Hazard ratio = 0.5757), 2 x 58 patients are to be randomized and 107 PFS events are needed if alpha error is 5% (0.05) and beta error is 20% (0.2). With a recruitment period of 18 months, a drop-out rate of 0.25% per month the 107 events are expected after a total follow-up time of 52 months assuming an exponential distribution.

Based on our data, the conversion rate is 80%. Assuming this conversion rate, 144 patients need to be screened to achieve 116 patients for the randomization. The screening will be continued until 116 patients are randomized.

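### Protocol 10.3 does not stratify its one confirmatory test, the PFS log-rank, by the randomisation factor; if run unstratified, it loses power should conversion time be prognostic

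*Protocol*

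**What the plan says.** Under "Stratification factors for randomization are", Protocol 3.1.2 lists a single item: conversion to RAS wild-type at 8 weeks or earlier versus later than 8 weeks. The same section ties this to timing. Early converters are randomised at week 8 and late converters at week 16, in both cases only if they have not progressed.

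Protocol 10.3 brings the factor into the analysis of time-to-event variables through a "Cox-regression model taking into account the following stratification factors". The log-rank test appears once, in the sentence that separates confirmatory from exploratory work: "All analyses except for the log-rank test for the primary endpoint will be of exploratory manner". That sentence does not mention the factor, and neither stratified nor unstratified is stated. The section leaves details to the SAP.

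The SAP does not settle the matter. Enrolment closed at seven patients (SAP 4.2). PFS is shown as a listing and a Kaplan-Meier plot (4.3.5), and covariates (4.14) and significance levels (4.19) are marked not applicable. No log-rank test is specified.

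**The concern.** The factor is named for one method and not for the other, a few lines apart, and the method without it is the only confirmatory one. Three things are at stake in the design.

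- **Power.** Omitting a prognostic factor pulls the estimated treatment effect towards no difference. The design has little reserve to absorb that.
- **Calibration.** When randomisation is balanced within strata and the strata differ in prognosis, an unstratified log-rank overstates its own variance and rejects less often than its nominal level.
- **Pre-specification.** In an open-label trial, leaving the version of the sole confirmatory test open allows the choice to be made after the data are seen. The test and a Cox estimate that uses the factor could also point in slightly different directions.

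Conversion time could well be prognostic. The two strata start the PFS clock at different points of first-line therapy and after different progression-free periods.

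**Working it through.** **Inputs from the protocol (Synopsis, 3.1.4, 10.4).** "With a two-sided alpha error of 5% (0.05) and beta error of 20% (0.2) 2 x 58 patients are to be randomized"; 12-month PFS of 30% versus 50%; 107 events; 18 months of recruitment; drop-out of 0.25% per month; 52 months in total; exponential PFS.

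**Step 1: the plan's own figures.**

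- Hazard ratio: ln 0.5 / ln 0.3 = 0.5757, as stated.
- Events, Freedman: (1.960 + 0.842)² × (1.5757 / 0.4243)² = 7.849 × 13.79 = 108.2, so 109.
- Events, Schoenfeld: 4 × 7.849 / (ln 0.5757)² = 103.
- The stated 107 lies between the two and within 3% of Freedman. Power at 107 events is 79.5% (Freedman) or 81.5% (Schoenfeld).
- Expected events per arm: 58 × λ/h × [1 − (e^(−h(T−R)) − e^(−hT)) / (hR)], with λ = −ln(S)/12, S the arm's 12-month PFS, h = λ + 0.0025, T = 52 and R = 18. Summed over both arms this gives 107.0.

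The sample size therefore reproduces, with no allowance for a stratum effect and almost no spare power.

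**Step 2: unstratified against stratified log-rank.** Each cell has 10,000 simulated trials of 116 patients, with permuted blocks of 4 within strata and a treatment hazard ratio of 0.5757 within each stratum. Control 12-month PFS is held at 30% overall; accrual, drop-out and duration are as above. Both tests are two-sided at 5%. Simulation error is about 0.4 points on power and 0.2 on type I error. The late-converter share and the stratum hazard ratio (late versus early) are **assumed**, because the documents give neither.

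| Stratum HR | Late share | Power unstratified | Power stratified | Gain (points) | Type I unstratified | Type I stratified |
|---|---|---|---|---|---|---|
| 1.0 | 20% | 81.0% | 80.0% | −0.9 | 5.7% | 5.8% |
| 1.0 | 35% | 80.6% | 79.4% | −1.2 | 5.1% | 5.2% |
| 1.0 | 50% | 80.1% | 79.1% | −0.9 | 5.3% | 5.4% |
| 1.5 | 20% | 79.7% | 80.2% | 0.5 | 5.2% | 5.3% |
| 1.5 | 35% | 78.8% | 79.7% | 0.9 | 5.4% | 5.7% |
| 1.5 | 50% | 78.6% | 79.6% | 1.1 | 4.7% | 5.0% |
| 2.0 | 20% | 77.3% | 79.5% | 2.2 | 4.8% | 5.4% |
| 2.0 | 35% | 75.7% | 80.0% | 4.3 | 4.2% | 5.1% |
| 2.0 | 50% | 74.6% | 79.5% | 4.8 | 4.0% | 4.9% |
| 3.0 | 20% | 74.3% | 79.6% | 5.3 | 4.4% | 5.1% |
| 3.0 | 35% | 69.3% | 78.3% | 9.0 | 3.4% | 4.8% |
| 3.0 | 50% | 65.6% | 78.7% | 13.1 | 3.4% | 5.2% |

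Gains are taken from unrounded figures. A separate simulation with late shares of 20% to 40% gave gains of about 0.5 to 1.5 points at 1.5, 2 to 5 at 2, and 5 to 11 at 3.

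**Step 3: where the loss comes from.** At a stratum hazard ratio of 2 and a 40% late share (4,000 runs), power was 74.2% unstratified versus 78.6% stratified, a gap of 4.4 points. Repeating this with randomisation *not* stratified by conversion gave 74.1% versus 78.4%, a gap of 4.3 points. The one-step log hazard ratio was −0.525 unstratified and −0.569 stratified. The loss therefore persists without stratified randomisation and is mainly attenuation. What stratified randomisation adds is the mild conservatism in the type I column.

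**The case against.** A reader might infer that the protocol prescribes an unstratified test. It does not. The log-rank sentence serves only to separate confirmatory from exploratory analyses, the factor is used in the preceding paragraph, and details go to the SAP. What stands is that the test is nowhere described as stratified, and that the SAP does not supply the missing statement.

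A reader might also take the power loss as certain. It depends on a prognostic effect that the documents do not quantify, and even its direction is open. Late conversion may mark a worse course, but late converters must also be progression-free at week 16 rather than week 8, which selects for a better one. These could offset each other. Protocol 2.4 notes that conversion can appear after a single chemotherapy cycle, so a small late share, and with it a small loss, cannot be excluded. With no stratum effect the unstratified test is about 1 point better. All of this stands, and is why the size is given as a range.

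Finally, one might blame the loss on an inflated standard error caused by ignoring the design's balance. Step 3 shows that this is the smaller part.

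**Conclusion.** The gap is real but modest. Protocol 10.3 does not stratify its only confirmatory test by the only factor used in randomisation, and the SAP specifies no log-rank test.

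If the test were run unstratified, the loss would be about 0.5 to 1.5 points of power at a stratum hazard ratio of 1.5, 2 to 5 at 2, and 5 to 13 at 3. Type I error would fall to about 4.0–4.8% at 2 and 3.2–4.6% at 3, taking both simulations together. At 1.5 or below it stays near 5%. These figures rest on exponential PFS, a constant treatment effect across strata, and late converters as the worse-prognosis group at 20% to 50% of patients. If early converters did worse, the worse-prognosis group could exceed 50%, which was not simulated.

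Two stronger conclusions are not supported. The validity of a positive result is not threatened, because a conservative test does not inflate type I error. Nor are the trial's reported results affected: with seven patients, SAP v2.0 runs no test. The point concerns the protocol as designed for 116 patients.

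**What to change.** In Protocol 10.3, state that the primary PFS comparison is a two-sided log-rank test at the 5% level, stratified by conversion to RAS wild-type (≤8 versus >8 weeks). State also that the hazard ratio comes from a Cox model stratified by the same factor, and that the unstratified log-rank test is a sensitivity analysis.

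This takes a sentence or two and needs no new data, since the factor is already used at randomisation. The statistical price is about 1 point of power if conversion time turns out not to be prognostic. The listings and Kaplan-Meier plots in SAP v2.0 stay as they are.
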